7.6.2 Safety/Tolerability

The safety analysis will be performed in the population valid for safety. All tabulations will be descriptive only.

The safety evaluation of laboratory data will include listings of laboratory data out of normal range, evaluation of the significance if they are out of normal range, descriptive analysis of continuous laboratory parameters and their changes from baseline by visit and treatment group. Vital signs will be summarized by visit and treatment group.

Clinical worsening (as exploratory safety endpoint) will comprise of the following parameters:

- worsening of WHO functional class
- deterioration of 6MWD >15% compared to baseline
- need of initiation of targeted PAH treatment
- hospitalization due to worsening of right heart function
- all cause death or lung-transplantation
- atrial septostomy

7.6.2.1 Adverse events

Tables will be produced for adverse events with a frequency $\geq 5\%$, drug-related adverse events and serious adverse events. Serious adverse events, adverse events with a frequency $\geq 5\%$ and drug-related adverse events will be displayed separately. In case of paired frequency data, analyses will be performed with McNemar Bowker test, or Wilcoxon signed rank test if preconditions are not met. Differences between therapy groups will be displayed by tabulation of results.

Mortality in the 24-week period of the study will be summarized descriptively. Any deaths in the study period will be listed, with day of death relative to start and stop of study drug and cause of death.

7.6.2.2 Laboratory parameters

Hematology	Leucocytes, erythrocytes, hemoglobin, hematocrit, platelets
Substrates	Bilirubin, cholesterol, triglycerides, creatinine, uric acid, urea, total protein, glucose
Electrolytes	Sodium, potassium, calcium, chloride
Enzymes	SGOT/ASAT, SGPT/ALAT, Gamma-GT, AP, LDH, CK
Others	INR, PTT, β -HCG test for women with childbearing potential at initial screening visit and visits 1, 3 and 5
Biomarkers	CRP, NT-proBNP

Efficacy laboratory will include analysis of N-terminal pro brain natriuretic peptide.

The safety evaluation of laboratory data will include:

Listings of laboratory data out of normal range, evaluation of the significance if they are out of normal range, descriptive analysis of continuous laboratory parameters and their changes from baseline by visit and treatment group.

7.6.2.3 Vital signs

Blood pressure, heart rate, SpO_2 will be analysed descriptively. Frequency of systolic blood pressure <95 mmHg will be displayed by group.

7.6.2.4 Pharmacokinetics

Not available

7.6.3 Exploratory analysis

Changes between baseline and 12 weeks, and between baseline and 24 weeks will be compared between groups by two-sided student's t-tests or Chi-square tests. For parameters see section 5.2.

7.7 Planned subgroup analyses

Subgroup analyses may not be performed due to insufficient sample size. In the original protocol, sensitivity analyses were planned including: investigation of the effect on patients with higher vs. lower PVR and higher vs. lower mPAP in case of sufficient sample size. Subgroup analyses by centre will be performed in case of sufficient sample size.

7.8 Interim analyses

Not available

8 Deviations from the original protocol

The study was ended prematurely, leading to a sample size reduction to 35 patients (planned 70 patients).

The study was terminated early due to a strategic decision of MSD/Merck:

“After reviewing the timelines, remaining payments, and considering the changing landscape and altered feasibility of this study, a strategic prioritization was made to select this study for early termination.”

As a result of this decision, the final sample size reached 50% of the originally planned enrolment (n= 35). All statistical analyses will be conducted based on the available data at the time of study cessation. The reduction in sample size may limit the statistical power, particularly given the double blinded two-armed design of the study. According to the study protocol, patients were encouraged to perform their final assessment visit in case of any premature termination of study treatment or study participation. This data will be included into the final analysis according to the intention-to-treat principle.

Subgroup analyses may not be performed due to insufficient sample size.

9 Interpretation of results

Interpretation of data is limited by the early termination of the whole trial. This led to a reduction of sample size to 35 patients in total instead of per group, and to a premature study termination in a subset of patients. As the treatment effect is anticipated to be less distinct in a shorter period of time in the verum group and worsening of clinical parameters is expected to be less pronounced in the control group, early study termination will reduce the effect size and does therefore not bear the risk of overestimation of the clinical effects of the study treatment. A shorter study duration is expected to reduce the statistical power (reduction of sample size and effect size).

Safety data will comprise of less investigational medicinal production exposition than planned. As the study medication is already an approved treatment and extensive data on safety and tolerability is already available, a substantial impact on safety and tolerability results of the study is not anticipated.

Due to the reduced sample size, subgroup analyses such as centre effects may not be further analysed as sample sizes for each center and for hemodynamics subgroups are not high enough.

10 Data problems

Analysis of PVR distribution identified an outlier at visit 3, which could be corrected by calculation of PVR from the formula $PVR = (mPAP - PAWP) / CO * 80$

PVR was therefore recalculated for all values at visit 3.

11 Software

Data analysis with SPSS V29, IBM Somers, New York.

12 References

NA

13 Appendices – List of Tables

All tables with mean \pm standard deviation or n and % for frequency data.

Tables with comparisons between groups will additionally include p-values and 95% confidence intervals.

Table 1. Demographics and Baseline Characteristics for the whole dataset and by group.

(table may be split for better readability)

Female sex no. [%]

Age [years]

Height [cm]

Weight [kg]

PH duration [months]

Vital

signs

Systolic blood pressure

Diastolic blood pressure

SpO₂ [%]

Heart rate

WHO FC no. [%]

I

II

III

IV

PAH Etiology

Idiopathic

Heritable

CTD-associated-PAH

Other

Concomitant diseases

Blood gas analysis

SaO₂ [%]

PaO₂ [mmHg]

PaCO₂ [mmHg]

pH

Bicarbonates

Hemodynamics at rest

RAP [mmHg]

sPAP [mmHg]

dPAP [mmHg]

mPAP [mmHg]

PAWP [mmHg]

CO [l/min]

CI [l/min/m²]

PVR [WU]

SvO₂ [%]**6MWD**

6MWD [m]

SpO₂ [%] test end

Borg dyspnea score

Short Form-36 Health Survey

Physical functioning

Physical role function

Pain

General health perception

Vitality

Social functioning

Emotional role function

Mental well-being

Physical summation score

Mental summation score

Echocardiography at rest

Estimated sPAP [mmHg]

RA area [cm²]RV area [cm²]

TAPSE [cm]

LV-EI

Left ventricular ejection fraction [%]

Lung function

FVC [L]

FEV1 [%predicted]

TLC [%predicted]

Residual Volume [%predicted]

DLCO % predicted

DLCO VA % predicted

Laboratory

Hemoglobin [g/dl]

Creatinine [mg/dl]

Urea [mg/dl]

Uric acid [mg/dl]

SGPT [U/l]

CRP [mg/l]

NTproBNP [pg/ml]

Table 2**Comparison of changes between groups****WHO FC Change (Visit 1-2)**

Improvement (- 1)

Worsening (+1)

Unchanged

Blood gas analysis

SaO2 [%]

PaO2 [mmHg]

PaCO2 [mmHg]

pH

Bicarbonates

Hemodynamics at rest

RAP [mmHg]

sPAP [mmHg]

dPAP [mmHg]

mPAP [mmHg]

PAWP [mmHg]

CO [l/min]

CI [l/min/m²]

TPR mmHg [min l- 1]

PVR [WU]

SvO2 [%]

6MWD

6MWD [m]

Short Form-36 Health Survey

Physical functioning

Physical role function

Pain

General health perception

Vitality

Social functioning

Emotional role function

Mental well-being

Physical summation score

Mental summation score

Echocardiography at rest

Estimated sPAP [mmHg]

RA area [cm²]RV area [cm²]

TAPSE [cm]

LV-EI

Left ventricular ejection fraction

[%]

LV-function improvement (+1)

LV-function unchanged

LV-function deterioration (-1)

Lung function

FEV1 [%predicted]

TLC [%predicted]

DLCO [% predicted]

Laboratory (V1-3)

NTproBNP [pg/ml]

Table 3

Safety analysis

All frequency data will be provided with n and %

- Tabulation of Adverse events (> 5 % of patients)
- Adverse events with suspected relation to the investigational medicinal product
- Serious adverse events

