6.5 Criteria for Removal or Withdrawal

6.5.1 Withdrawal of Subjects

A subject will be withdrawn from the trial treatment for the following reasons:

1. at their own request or at request of their legal representative
2. if, in the investigator's opinion, continuation of the trial would be detrimental to the subject's well-being
3. occurrence of a severe serious adverse event (SAE) caused by the IMP
4. The participant has a medical condition or personal circumstance which, in the opinion of the investigator placed the participant at unnecessary risk from continued administration of study treatment. This includes progression or aggravation of the pulmonary hypertension, so that appropriate PAH targeted therapy may be introduced without delay.
5. The participant has a confirmed positive serum pregnancy test.

The Coordinating Investigator decides about withdrawal of subjects from trial treatment in case of occurrence of criteria mentioned above.

Patients with a serious adverse event occurring during the study treatment will be followed by the study team until the serious adverse event will have resolved to the pre-study level and/or will have been addressed according to best clinical practice. The patient, either willingly withdrawn from the study or due to premature termination, will be asked thoroughly to complete all examinations scheduled for the final trial day, and these will be performed as far as possible and documented.

In all cases, the reason for withdrawal must be recorded in the CRF and in the subject's medical records.

In case of withdrawal of a subject at his/ her own request, the reason should be asked for as extensively as possible and documented.

All efforts will be made to follow up the subject.

A subject may/ will be withdrawn from all trial related procedures (including follow-up visits) for the following reasons:

- at his/her own request or at request of his/her legal representative
- non-adherence to the trial-related requirements, which may (have) influence(d) the validity of the trial data

EudraCT: 2021-001633-40	Version 1.7 15.01.2025	ESRA
-------------------------	---------------------------	------

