1.3 Randomisation, stratification, blinding and replacement of patients

Randomisation was performed by permuted block randomization, stratified by centre. Treatment was allocated by consecutive patient numbers for each centre with respective blinded medication included in the investigational medicinal product packages for each visit.

Patients and investigators were blinded to treatment assignment. The statistician will be blinded to treatment assignment during the statistical analysis. In case of dropout, loss to

follow-up, early withdrawal or other cases of incomplete data, patients were not replaced. However, patients were encouraged to perform their final assessment in case of early termination or withdrawal. The results will be included in the analysis.

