- RHC*	- Initiation of study drug***					
- Adverse Events	- Adverse Events					

* RHC at screening only in patients who have not had a RHC within a month before OR within the preceding 6 months if clinically stable as stated
** not if already performed at Screening AND if Screening and Baseline are conducted during same hospital stay

***Titration Plan:
individual dosing titration

Overview of visit assessments

Assessments	Double-blind						
	Screening	Visit 1 Baseline	V 1.1-1.4 Phone Visits Titration	Visit 2 Interim visit	V 2.1-2.2 Phone Visits Only WOCBP	Visit 3 Termination visit	Visit 4 Safety FU
	-28 days	Day 1	Week 2, 4, 6 and 8 ±2 days	Week 12 ±7 days	Week 16 and 20 ±2 days	Week 24 ±14 days	30 days after last IMP intake ±14 days
Informed Consent	1	-	-	-	-	-	-
Inclusion / exclusion criteria	1	1	-	-	-	-	-
Patient diary(handing out / compliance check)	-	1	-	1	-	1	-
Prior and concomitant medication	1	1°	4	1	2	1	1
Demography, height and medical history	1	-	-	-	-	-	-
PAH classification, etiology, diagnosis date	1	-	-	-	-	-	-
WHO-FC	-	1	-	1	-	1	-
Vital signs, incl. heart rate, SpO ₂ (%)	1	1	-	1	-	1	-
6MWD, Borg Dyspnea Score	-	1	-	1	-	1	-
Weight	1	1°	-	1	-	1	-
ECG	1	1°	-	1	-	1	-
Blood gas analysis	1	1°	-	-	-	1	-
Lung function testing (Plethysmography)	1	1°	-	-	-	1	-
Diffusing capacity of the lung	1	1°	-	-	-	1	-
Right heart catheter	1*	-	-	-	-	1	-
Physical examination	1	1°	-	1	-	1	-
Laboratory Hematology, Chemistry, Hemostaseology, NT-proBNP	1	1°	-	1	-	1	-
Pregnancy test (only WOCBP)	1	1°¶	2+ (week 4 and 8)	1	2+ (week 16 and 20)	1	1+
Echocardiography	-#	1#	-	-	-	1	-
Quality of life (SF-36)	-	1	-	-	-	1	-
Adverse Events	1	1	4	1	2	1	1
Systolic blood pressure and dose adjustment	-	-	4	-	-	-	-
Drug dispensed	-	1	-	1	-	-	-
Drug collected	-	-	-	1	-	1	-
Drug compliance	-	-	-	1	-	1	-
Phone visits	-	-	4	-	2	-	1

* RHC at screening will only be performed in patients who have not had a RHC within the preceding 1 month at screening. A preceding RHC from the last 6 months can be used if the patient had no signs of clinical changes defined as change of 6MWD >10%, WHO-FC change or >30% change in NT-proBNP. RHC must have been measured in the participating center under standardized conditions.

+ Pregnancy test at home.

¶ Handing out pregnancy tests for home use

° Will not be performed if already performed at Screening AND if Screening and Baseline are conducted during same hospital stay.

† Optional during the SARS-CoV2-pandemic.

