5.1 Efficacy Variables

The primary efficacy variable is the change of PVR from baseline to 24 weeks.

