7.5 Primary analysis

Null-Hypothesis (H_0):

The means of the treatment and control group of the primary endpoint is the same at baseline and after 24 weeks.

Alternative hypothesis (H_1):

The mean of the treatment group of the primary endpoint after 24 weeks differs from the mean of the control group.

Type I error

If not mentioned otherwise, all statistical tests will be performed with a type I two-sided error rate of $\alpha = 0.05$

The evaluation of the primary efficacy endpoint will be the change from baseline to 24 weeks in pulmonary vascular resistance. The primary analysis set will be a complete case analysis of the intention-to-treat set.

The main comparison will be the difference in treatment effect between riociguat (MK-4836) and placebo. 95% confidence intervals of treatment difference will also be calculated. The primary comparison will be an ANCOVA model including baseline scores as covariate.

If the preconditions for an ANCOVA analysis are not met, the primary endpoint will be analyzed by robust, two-sided t-test (Welch-test).

A multiple imputation strategy will be implied and analyzed for the primary endpoint (25 imputations) in case of missing data for the primary endpoint.

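### No planned analysis shows the week-24 PVR result without catheterisations done before the Visit 3 window, and SAP 9 is wrong to exclude overestimation outright

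*SAP*

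**What the plan says.** - **Endpoint and window.** SAP 5.1: "The primary efficacy variable is the change of PVR from baseline to 24 weeks". The visit overview in SAP 4 places Visit 3, which includes the RHC, at "Week 24 ±14 days".
- **Primary analysis.** SAP 7.5 specifies a complete-case ANCOVA in the intention-to-treat set. It has no sentence on RHCs done before the window. On imputation it says: "A multiple imputation strategy will be implied and analyzed for the primary endpoint (25 imputations) in case of missing data for the primary endpoint".
- **Early final assessments.** Under Protocol 6.5.1 a patient who leaves early "will be asked thoroughly to complete all examinations scheduled for the final trial day". SAP 1.3 says: "However, patients were encouraged to perform their final assessment in case of early termination or withdrawal. The results will be included in the analysis". SAP 8 bases all statistical analyses on the data available when the study ceased, and then says of these final assessments: "This data will be included into the final analysis according to the intention-to-treat principle".
- **Early stopping happened.** SAP 9 reports "premature study termination in a subset of patients" but gives no number, timing or arm.
- **Interpretation.** SAP 9 expects a weaker treatment effect and less worsening on placebo over a shorter time, and concludes that "early study termination will reduce the effect size and does therefore not bear the risk of overestimation of the clinical effects".
- **Per-protocol set.** Protocol 10.2 required an adequate PVR at week 24, or an earlier one only after withdrawal for lack of efficacy. SAP 2.1 no longer has this requirement.

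**The concern.** The primary estimate carries a 24-week label but can combine PVR values taken after quite different exposure times. A patient stopped by the sponsor's decision at, say, week 10 may not have been long on a maintenance dose, since titration alone takes 8 weeks. Pooling such values can be defended, but a reader would want to see how far they move the result, and nothing in the SAP would show it.

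The clause in SAP 9 is a separate matter. It is interpretation written before the result is known. If it stands, a statistically significant difference from 35 patients could be presented as conservative, although at this size a significant estimate is expected to exceed the true effect.

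**Working it through.** **Does any planned analysis separate early values?**

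- Multiple imputation (SAP 7.5) acts only on missing primary data. An early RHC that counts as the week-24 value is not missing.
- The outlier analysis (SAP 6.2) removes values beyond 3 × the interquartile range, whatever their timing.
- The per-protocol set (SAP 2.1) excludes failures of the inclusion criteria and IMP use not according to protocol, for example compliance below 80%. It removes an early stopper only if compliance is counted against the planned 24 weeks, which the SAP does not say. The protocol's version would have removed patients stopped for strategic reasons.

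None does so reliably.

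**Inputs for the arithmetic.** From Protocol 10.1 and SAP 5.1.1: difference 30 points, SD 34.5, two-sided α = 0.05, 29 evaluable per arm, power 90.2%. From SAP 8: 35 patients. Assumed: an 18/17 split, all 35 evaluable, an unadjusted t-test as in the plan's own power calculation.

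**Reproducing the plan.** Effect size = 30/34.5 = 0.870. SE = 34.5 × √(1/29 + 1/29) = 9.06. Noncentrality = 30/9.06 = 3.31 on 56 df. Power = 90.2%, as stated.

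**At 18/17.** SE = 34.5 × √(1/18 + 1/17) = 11.67. Noncentrality = 30/11.67 = 2.57 on 33 df. Power = 70.4%.

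**Exaggeration** is the mean of |estimate| among results with p < 0.05, divided by the true 30. It was found by integrating over the sampling distributions of the difference and of the variance estimate.

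| Evaluable | Power | Smallest significant difference (SD 34.5) | Exaggeration |
|---|---|---|---|
| 29/29 | 90.2% | 18.1 | 1.06 |
| 18/17 | 70.4% | 23.7 | 1.185 |
| 15/15 | 63.3% | 25.8 | 1.24 |
| 14/13 | 58.3% | 27.4 | 1.28 |

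**Adding early values.** Suppose k of the 18 active values are early and carry a share r of the 24-week effect, with the placebo mean unchanged. The mean estimate relative to the 24-week effect is 1 − (k/18)(1 − r). For k = 4 and r = 0.5 this is 1 − 0.222 × 0.5 = 0.89, a mean of 26.7 points. The chance that the estimate exceeds 30 is P(Z > (30 − 26.7)/11.67), about 39%, against 50% with no early values. Power and exaggeration are by simulation at 18/17:

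| k | r | Mean ratio | Power | Exaggeration against the 24-week effect |
|---|---|---|---|---|
| 2 | 0.75 | 0.97 | 68% | 1.17 |
| 4 | 0.50 | 0.89 | 59% | 1.13 |
| 7 | 0.75 | 0.90 | 61% | 1.14 |
| 7 | 0.25 | 0.71 | 40% | 1.07 |

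Over k = 2, 4, 7 and r = 0.25, 0.5, 0.75, the mean ratio runs from 0.71 to 0.97 and the exaggeration from 1.07 to 1.17. So dilution lowers the average estimate, as SAP 9 says, while significant estimates still average above the true 24-week effect in every case examined.

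**The case against.** **Inclusion is largely settled.** A reader might infer that the SAP leaves open whether early RHCs enter the primary analysis. The documents do not support that. SAP 8 applies all analyses to the available data and adds the early final assessments, SAP 1.3 agrees, and the dilution argument in SAP 9 presupposes it. What SAP 7.5 lacks is a confirming sentence. Nor is the mixture hidden: SAP 9 says that a subset stopped early and that a smaller effect is expected.

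**SAP 9 is about direction.** Its stated reason is time, and on average direction it is reasonable. A reader might go further and infer that early termination biases the result upward. The documents do not support that either. The stop is described as strategic and no interim analysis is reported, so there is no data-driven stopping bias. The premise that the effect grows with time has some support: the bosentan cohort in Protocol 7.3 (ten patients, another drug, before-after) and the further 6MWD gain in 215 riociguat patients in Protocol 2.1 and 7.2 (uncontrolled, not PVR). The 12-week effect size of 0.94 in SAP 5.1.1 exceeds the assumed 0.87, but it is a before-after figure in established PAH and does not show that the effect shrinks with time.

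**Exaggeration among significant results affects any trial with power below 100%.** True: it is 1.06 even at the planned size. SAP 8 and 9 also disclose the loss of power. Neither point rescues a statement that there is no such risk, because halving the sample is part of the same early termination and raises the figure.

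**The size rests on assumptions.** Also true. ANCOVA would lower the ratio: if baseline explained 9% to 25% of the variance (assumed), 1.185 becomes 1.16 to 1.10. Dropouts would raise it, to 1.24 at 15/15.

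**Conclusion.** The point holds in two parts, and both should be fixed.

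1. Pre-window RHCs most likely enter an estimate labelled as change to 24 weeks, and no planned analysis shows the result without them. Their effect cannot be sized from the documents, because the number, timing and arm of early RHCs are not given.
2. The SAP 9 clause is sound as an expectation about average direction if the effect grows with time, and wrong as an absolute. At 18/17 with all 35 evaluable and an unadjusted t-test, power is about 70% and significant estimates average about 1.185 times the truth. With early values in the assumed range the figure is 1.07 to 1.17.

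The arm split, full evaluability, the number of early values and the share of effect they carry are assumptions. The existence of the exaggeration depends only on power being well below 100%.

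**What to change.** Before unblinding:

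1. **SAP 7.5.** Keep the all-values analysis as primary and say so in one sentence: a final RHC done before the Visit 3 window counts as the week-24 PVR, and the patient is a complete case. Add one sensitivity analysis of the primary endpoint restricted to RHCs within 24 weeks ±14 days. Report the number and timing of pre-window RHCs by arm.
2. **SAP 9.** Replace the overestimation clause with: *Early values may dilute the effect on average; at this sample size a statistically significant estimate may nevertheless be larger than the true effect.*

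The cost is two sentences, one analysis and one table line. The downside is that the in-window analysis has fewer patients and lower precision. If four values per arm were early (14/13), its power would be 58%, against 59% for all values with k = 4 and r = 0.5, and its significant estimates would average 1.28 times the truth. Over the assumed range, with equal numbers early in both arms, its power runs from 7 points above to 14 points below the all-values analysis. It should therefore be supportive only.

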7.2 Therapeutic Effects

Pulmonary arterial hypertension is defined by an increased mean pulmonary arterial pressure and pulmonary vascular resistance. Patients with systemic sclerosis or other forms of connective tissue disease have an increased risk to develop pulmonary arterial hypertension which significantly impairs their prognosis.

Riociguat is the first drug that has been approved for the treatment of both PAH and CTEPH (Ghofrani et al. 2013). The 12-week PATENT-1 study showed a significant improvement of the

EudraCT: 2021-001633-40	Version 1.7 15.01.2025	ESRA
-------------------------	---------------------------	------

primary endpoint 6MWD and of secondary endpoints such as PVR, NT-proBNP levels, WHO-FC, time to clinical worsening and Borg dyspnea score (Ghofrani et al. 2013). An exploratory analysis of the first 12 weeks of the long-term extension study (PATENT-2) showed further significant improvement of 6MWD in the 215 PAH-patients receiving up to 2.5 mg of riociguat tid (Rubin et al. 2015).

In CTEPH-patients the 12-week CHEST-1 study revealed a statistically significant improvement of 6MWD (primary endpoint) and in PVR, NT-proBNP serum values, and in WHO-FC (secondary end points) (Ghofrani, et al. 2013). Further studies investigating the effect of riociguat in an uncontrolled design were the early access study (EAS) in patients with CTEPH (McLaughlin et al. 2017) and PATENT plus in PAH (Galiè et al. 2015).

In a retrospective analysis of patients with CTD-APAH receiving riociguat in PATENT-1 and PATENT-2, mean improvement of PVR after 12 weeks was 132 ± 140 dynes*sec*cm $^{-5}$ in patients with SSc (equals 1.65 ± 1.75 WU).

Up to now, it is not known, whether targeted treatment for PAH provides a benefit in patients with early pulmonary vascular disease.

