8.2.2 Hemodynamic parameters

Hemodynamic parameters will be determined by right heart catheterization according to current guidelines (Opitz et al. 2011). The right heart catheterization (RHC) will be performed at screening only in patients who have not performed a RHC within the preceding 1 month or in the last 6 months if the patient had no signs of clinical changes defined as change of 6MWD >10%, WHO-FC change or >30% change in NT-proBNP. RHC must have been measured in the participating center under standardized conditions. RHC may involve exposure to ionising radiation only if clinically indicated.

Directly, invasively measured parameters are: CI, sPAP, mPAP, dPAP, PAWP, RAP, PVR, CO, SvO₂. During the right heart catheterization, a continuous ECG will be performed. The values will be based on three measurements at one time point. The three values of CO should not differ by more than 10% from each other. Optionally, arterial blood gas saturation can be measured in wedge position.

Directly non-invasive measured parameters: heart rate, blood pressure

Methodology: Swan-Ganz catheterization and thermodilution methodology

The primary endpoint PVR (in WU) will be calculated by the formula PVR = (mPAP-PAWP)/CO*80. CI (in l/min/m²) will be calculated by CO/Body mass area.

The data will be directly measured in the participating centers and will be transferred to the CRF. In addition, RHC recordings will be centrally read by two experienced physicians who are blinded

EudraCT: 2021-001633-40	Version 1.7 15.01.2025	ESRA
-------------------------	---------------------------	------

to study treatment. Original RHC data will be submitted for central reading with pseudonymized pressure curves and data of thermodilution.

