10.1 Sample Size Calculation

In this randomized study patients with early pulmonary vascular disease, indicated by either a) mPAP ≥ 25 mmHg with PVR ≥ 2 to < 3 WU and PAWP ≤ 15 mmHg or b) mPAP 21- < 25 mmHg with PVR ≥ 2 WU and PAWP ≤ 15 mmHg will be randomized into two groups: one group receiving riociguat (MK-4836) and one placebo group.

In the EDITA study (Pan et al. 2019) SSc patients with mildly elevated mPAP 21-24 mmHg showed a significant reduction of PVR after 6 months of treatment (control-group 0.02 ± 0.76 vs. intervention group -0.59 ± 0.79 WU; effect size 0.77). The changes in PVR were equal to a $23.87 \pm 35.68\%$ reduction in the intervention group and increase by $5.44 \pm 36.61\%$ in the control group (effect size 0.81).

A meta-analysis showed an effect size of 0.88 in both PAH and CTEPH (Zhao et al. 2019).

In the retrospective analysis of patients with CTD-APAH receiving riociguat in PATENT-1 and PATENT-2, mean improvement of PVR after 12 weeks was 132 ± 140 dynes*sec*cm $^{-5}$ in patients with SSc (equals 1.65 ± 1.75 WU; effect size 0.94; Humbert et al. 2017). Patients with SSc-PAH had an effect size of 0.97 (Humbert et al. 2017).

EudraCT: 2021-001633-40	Version 1.7 15.01.2025	ESRA
-------------------------	---------------------------	------

In this study, patients with PVR \geq 2WU will be included. The use of the effect size of the EDITA study for sample size calculation leads most likely to an underestimation of the effect, as in this study with ambrisentan most patients showed a PVR <2 WU at baseline. Furthermore, all studies reported in the table below had a study duration of 12 weeks. A study duration of 24 weeks will lead to a higher effect and reduction of PVR. Therefore, we assume an effect size of 0.87 of riociguat (MK-4836) treatment in this study. A comparable effect size for both included subgroups is anticipated for this study.

Reference	Change / difference in PVR	Effect size	Power	Sample size without dropout
Pan 2019; EDITA	SSc: 0.61 \pm 0.79 WU (Ambrisentan)	0.77	80%	56
Pan 2019; EDITA	SSc: -23.87 \pm 35.68% (n=17) in the intervention group and increase by 5.44 \pm 36.61% (n=15) in the control (Ambrisentan)	0.81	90%	66
Zhao 2019 Meta-analysis Riociguat	PH (PAH and CTEPH): n=695 (Riociguat)	0.88	85%	50
Humbert 2017 CTD-APAH from PATENT-1 and 2	SSc: 1.65 \pm 1.75 WU Other CTD: 3.45 \pm 3.54 WU (Riociguat)	0.94 0.97	90% 90%	50 48
A sample size of 58 will lead to n=70 with dropout of 15%.				

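### The PVR formula labelled WU carries a factor of 80 that gives dyn·s·cm⁻⁵, and the SAP reports recalculating PVR at visit 3 without saying whether baseline was treated the same way

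*SAP*

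**What the plan says.** Protocol 8.2.2 states: "The primary endpoint PVR (in WU) will be calculated by the formula PVR = (mPAP-PAWP)/CO*80". The formula is not limited to a visit. The same section also lists PVR among the directly measured parameters, so a recorded PVR can exist beside its components.

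SAP section 10 (Data problems) reports: "Analysis of PVR distribution identified an outlier at visit 3, which could be corrected by calculation of PVR from the formula", followed by the same formula with the factor 80. It then says: "PVR was therefore recalculated for all values at visit 3". Baseline is not mentioned there, and no other SAP section says how baseline PVR was derived or checked.

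Everything else about PVR is in WU: the entry limits of 2 and 3 WU (Protocol 6.3, SAP 2.1) and the rows headed PVR [WU] in SAP Tables 1 and 2. Protocol 7.2 and 10.1 convert 132 ± 140 dyn·s·cm⁻⁵ to WU ("equals 1.65 ± 1.75 WU").

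The endpoint is the change in PVR from baseline to week 24. For its analysis, SAP 7.5 says: "The primary comparison will be an ANCOVA model including baseline scores as covariate". If the ANCOVA preconditions fail, a Welch test replaces it.

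On the source of the components, Protocol 8.2.2 says "The data will be directly measured in the participating centers and will be transferred to the CRF" and adds: "In addition, RHC recordings will be centrally read by two experienced physicians who are blinded" to treatment.

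**The concern.** There are two gaps, both in the definition of the sole primary endpoint.

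**Unit.** The only PVR formula in either document does not produce the unit it is labelled with. SAP section 10 says this formula was applied to trial data, so a reader cannot tell from the text whether the recalculated visit 3 values are in WU or in dyn·s·cm⁻⁵. If the formula were followed literally, entries labelled WU could not be read against the 2 and 3 WU limits.

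**Baseline.** A change score needs the same quantity at both ends. The visit 3 correction shows that at least one stored PVR disagreed with its own components, so having a formula in the protocol did not guarantee that stored values followed it. The remedy is reported for one of the two time points. Baseline PVR is the other half of the change score and is also the covariate. With 35 patients, individual values carry weight.

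**Working it through.** **1. The documents' own conversion.** 132/80 = 1.65 and 140/80 = 1.75. The stated figure reproduces exactly, so 1 WU = 80 dyn·s·cm⁻⁵.

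**2. What the printed formula returns.** Take mPAP 23 mmHg, PAWP 10 mmHg and CO 5.2 l/min (assumed).
- Without the factor: (23 - 10)/5.2 = 2.5, which is WU.
- As printed: 2.5 × 80 = 200, which is dyn·s·cm⁻⁵.
- With the 80 in the denominator: 13/(5.2 × 80) = 0.031, which is not WU either.
- The entry range of 2 to <3 WU would become 160 to <240.

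**3. Effect if both visits use the printed formula.** Change and covariate are both multiplied by 80. Test statistics, p-values and percent changes stay the same. The estimate, its confidence interval and every tabulated PVR are 80 times the WU value.

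**4. Effect of a same-unit difference in derivation.** Assumed inputs:
- 17 and 18 patients (the SAP gives 35 in total, not the split);
- baseline mean 2.5 WU, baseline SD 0.4 to 0.6 WU;
- SD of change 0.345 × 2.5 = 0.8625 WU and effect 0.30 × 2.5 = 0.75 WU, taking the planned 34.5% and 30% at that baseline;
- visit 3 PVR rising by no more than 1 WU per WU of baseline (slope at most 1).

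*Random baseline noise, SD 0.15 WU (assumed).* Adjusting for a noisy baseline adds b²·S²τ²/(S²+τ²) to the residual variance, with slope b, baseline SD S and noise SD τ. At b = 1 the residual variance is 0.8625² = 0.7439.
- S = 0.4: 0.16 × 0.0225/0.1825 = 0.0197. The SE ratio is √(1 + 0.0197/0.7439) = 1.013.
- S = 0.6: 0.36 × 0.0225/0.3825 = 0.0212. The SE ratio is √(1 + 0.0212/0.7439) = 1.014.

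Simulation (3,000 runs per setting, 17 against 18) gave a rise of at most 1.3% in the settings with slope at most 1.

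*One baseline value wrong by 1 WU (assumed).* The Welch difference moves by 1/18 = 0.056 or 1/17 = 0.059 WU, and 0.059/0.75 = 7.8% of the assumed effect. With fewer complete cases the shift is 1/n for the arm concerned. In the simulation the ANCOVA estimate moved by 0.019 to 0.053 WU on average.

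**5. What is untouched.** The sample size uses percent change, so the stated 90.2% power does not depend on this point.

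**The case against.** The case for treating this as wording only is substantial.

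- *The unit is probably notation.* Entry limits, the absolute inputs to the sample size and the tables all use WU. This stands as the likeliest explanation, but the stated rule for the primary endpoint is still wrong as written.
- *The silence on baseline has an innocent reading.* SAP section 10 logs problems; it is not a derivation section. Its check of the PVR distribution is not described as limited to one visit, and the protocol formula nominally covers baseline. Baseline values also had to pass entry limits, which visit 3 values did not. All of this makes a gross baseline error less likely. None of it says that baseline was derived or checked from components.
- *SAP 6.2 plans a sensitivity analysis without extreme outliers.* This guards only against gross errors. For a normal change with SD 0.8625 WU the interquartile range is 1.349 × 0.8625 = 1.16 WU, and three times that is 3.49 WU. A 1 WU error would not by itself reach that threshold.
- *The source is mostly settled.* SAP 1.4 describes CRF data entered into the database, and Protocol 8.2.2 presents central reading as additional. The plain reading is site CRF values; one confirming sentence is enough.

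A reader might infer that visit 3 is in dyn·s·cm⁻⁵ while baseline is in WU. The ANCOVA p-value would then be unchanged, because multiplying visit 3 by 80 multiplies both the treatment coefficient and its SE by 80. The estimate would be 80 times too large, and the Welch fallback would in effect compare visit 3 levels. The documents do not support this. The formula is reported to have corrected a single outlier, which fits poorly unless its output was on the scale of the other stored visit 3 values.

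A reader might also infer a treatment-dependent correction. Nothing suggests one: SAP 1.3 keeps the statistician blinded during the analysis.

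**Conclusion.** The unit conflict is certain from the documents: the formula labelled WU returns 80 times the WU value. Whether any data are affected is not shown. If both visits are handled alike, inference and percent changes are safe, and only the WU-labelled values, estimate and interval would be wrong.

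The gap on baseline is also real, as a missing statement and not as a demonstrated error. Its expected effect is small: about 1.3% on the standard error for the assumed noise, and about 0.06 WU on the Welch difference for one assumed 1 WU error. The noise level, error size, baseline distribution and arm split are assumptions; the documents give none of them. Materially larger losses of precision would need slopes near 2 or above, which are implausible.

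One might be tempted to turn the single outlier into a mismatch rate for baseline. The documents do not allow it. They give neither the number of discrepancies found on recalculation nor the number of visit 3 catheterizations, and SAP section 9 says that some patients stopped early.

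Severity is minor to should-fix. The numerical risk is low, but this is the definition of the sole primary endpoint and the repair is almost free.

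**What to change.** 1. In Protocol 8.2.2 and SAP section 10, state PVR [WU] = (mPAP-PAWP)/CO. If stored values are in dyn·s·cm⁻⁵, say so and state the division by 80 used for the tables.
2. Before unblinding, derive PVR by that one formula at baseline and visit 3 for every patient, from the same source of mPAP, PAWP and CO. Confirm in one sentence that the source is the site CRF.
3. Use these values for both the change score and the ANCOVA covariate.
4. List recorded against recalculated PVR at both visits, with the reason for each discrepancy.

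The cost is a line or two of text in each document, a few lines of derivation code and one listing. The components come from the catheterizations already required at baseline and visit 3, so no new data are needed.
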